**Schedule of Assessments / Q8 Week Arms (NGM621 and Sham)**

*Study flowchart for Q8W Arms: Day 1, Week 1, Week 4 through Week 56*

Activity/Assessment	Screen	Baseline	Treatment															Follow Up	
	Day -28 to Day -3	Day 1	Wk 1	Wk 4	Wk 8	Wk 12	Wk 16	Wk 20	Wk 24	Wk 28	Wk 32	Wk 36	Wk 40	Wk 44	Wk 48	Wk 52	EOT 	Wk56	EOS
Month				M1	M2		M4		M6		M8		M10		M12	M13	M14		
Visit Windows			±3	±5	±5	±5	±5	±5	±5	±5	±5	±5	±5	±5	±5	±5	±5		
Informed Consent	X																		
Inclusion/Exclusion criteria	X																		
Demographics	X																X		
Ocular/Medical History	X																		
Physical Exam	X																X		
Body Weight	X																X		
Pregnancy Testing 	X	X															X		
Blood Sample (Hematology, chemistry) 	X																X		
Urine Sample (Urinalysis, Drug Screen)	X																		
Adverse Events 	X	X	X	X	X	X	X	X	X	X	X	X	X	X	X	X	X		

Concomitant Medications	X	X	X	X	X	X	X	X	X	X	X	X	X	X	X	X	X	X	X
Vital Signs	X								X									X	X
FRI Index 		X							X									X	
NEI VFQ-25 		X							X									X	
BCVA	OU	OU	OU	OU	OU		OU	OU	OU										
LLVA	OU								OU								OU		
Reading Speed		X							X									X	
Pre- and Post-dose IOP 	OU	OU	SE		SE		SE		OU		SE		SE		SE		OU	OU	OU
Slit lamp Biomicroscopy	OU	OU	OU	OU	OU		OU	OU	OU										
Dilated Fundus Exam and Indirect Ophthalmoscopy	OU	OU	OU	OU	OU		OU	OU	OU										
SD-OCT 	OU						OU		OU		OU		OU				OU	OU	
Fundus Autofluorescence (FAF) 	OU								OU									OU	
Fluorescein angiography (FA) 	OU																		
Color Fundus Photography (CFP)	OU																	OU	
Microperimetry at select sites (Study eye only) 	SE	SE							SE									SE	
Serum PK 		X	X	X	X		X		X				X		X		X	X	X
Serum ADA 		X		X	X		X		X				X		X		X	X	X
Serum NAb 		X		X	X		X		X				X		X		X	X	X
Serum – C3 and CH50		X	X	X					X								X	X	X
CCI																			
Randomization			X																

Optional Buccal Swab for genetic testing 		One-time collection at any visit from Day 1 to EOS. Collect only if subject has consented to optional procedure.
Dosing (please see Table 6)		

OU = both eyes; SE = study eye; X = Required

 Females of childbearing potential only; Serum pregnancy test to be conducted at screening. Urine pregnancy test to be conducted on Day 1 and Week 48 visit. If pregnancy is suspected, a serum pregnancy test may be conducted.

 For the screening visit only, it is allowable to draw blood in the order of assessments as listed in the table OR the blood draw can occur right before the FA assessment to allow for a single needle stick.

 Columns shaded gray indicate that adverse event reporting will be by telephone (📞) for non-visit months (Weeks 12, 20, 28, 36, and 44) for subjects in the Q8W arm only.

 The patient-reported outcome (PRO) measures (NEI VFQ-25 and FRI Index) will be administered by the masked site staff (except for the VA examiner) prior to any other visit assessments being performed.

 Reference [Section 7.3.12.1](#) and the pharmacy manual for details.

 A FA and SD-OCT should be performed if the development of CNV is suspected in study eye. The central reading center must confirm this finding before any intervention is initiated. See [Section 7.3.15](#) for details.

 After randomization, if a patient misses a study visit when FAF images were scheduled to be taken, the images should be taken at the next scheduled visit.

 Microperimetry is optional and applies to select sites.

 PK, Anti-drug antibody and neutralizing antibody samples will be collected Day 1 pre-dose, Week 1 post-dose (PK collection only), Week 4 post-dose, Weeks 8, 16, 24, 40, 48 pre-dose, and Weeks 52 and 56.

 For subjects who discontinue early from the study, the EOT visit assessments should be performed after a minimum of 28 days has elapsed from the last administered dose. See [Section 6.7](#) for details.

 For subjects who consented to the optional sample collection.

Schedule of Assessments / Dosing Treatment Arms	Treatment Arm	Screen	Baseline	Treatment												Follow Up	
		Day -28 to Day -3	Day 1	Wk 1	Wk 4	Wk 8	Wk 12	Wk 16	Wk 20	Wk 24	Wk 28	Wk 32	Wk 36	Wk 40	Wk 44	Wk 48	
	NGM621 15 mg Q4W		X 		X 												
	Sham Q4W		X 		X 												
	NGM621 15 mg Q8W		X 			X 											
	Sham Q8W		X 			X 											

 Refer to [Section 7.3.12.1](#) and the pharmacy manual for details on treatment administration and pre- and post-dose IOP monitoring, and if needed, IOP management instructions.

---

Statistical Methods	Analysis Sets
	

• Modified Intent-To-Treat (mITT) Analysis Set: All randomized and treated (with at least one dose of study drug) subjects. This analysis set will be used for all efficacy analyses and subjects will be analyzed based on the treatment group into which they are randomized.

• Per Protocol (PP) Analysis Set: A subset of subjects in the mITT Analysis Set who have no protocol deviations that affect the GA lesion assessments (by FAF). This analysis set will be used for sensitivity analyses to support the mITT analyses.

• Safety Analysis Set: All treated subjects. This analysis set will be used for all safety analyses and subjects will be analyzed based on the actual treatment they receive.

• Pharmacokinetic (PK) Analysis Set: A subset of subjects in the Safety Analysis Set who have quantifiable PK measurements post first dose. This analysis set will be used for all PK analyses and subjects will be analyzed based on the actual treatment they receive.

### **General Statistical Considerations**

In general, descriptive statistics including the number of non-missing observations (n), arithmetic mean (mean), standard deviation (SD), median, minimum (min), and maximum (max) will be presented by treatment group for continuous variables. Frequency and percentage distribution will be presented by treatment group for categorical variables.

### **Primary Efficacy Analyses**

#### *Primary Estimand*

The estimand for the primary interest of this study is defined as follows:

1. Treatment: NGM621 Q4W, NGM621 Q8W, and pooled Sham (Sham injections Q4W or Q8W).
2. Population: subjects with geographic atrophy secondary to age-related macular degeneration as defined by the inclusion-exclusion criteria of the study.
3. Endpoint: rate of change in GA lesion area as measured by FAF over the 52 weeks of treatment.
4. Inter-current events and their corresponding strategies: see [Section 8.3.1.1](#).

5. Population-level summary: the treatment group difference between each NGM621 group and the pooled Sham group in the mean change from baseline to Week 52 in the GA lesion area as measured by FAF.

### ***Main Estimation***

The GA lesion area (at baseline, Week 24, and Week 52) will be analyzed using a random coefficients model. The model includes terms for time (continuous variable assuming linearity) and treatment-by-time interaction. The intercept and slope of time are assumed to be random effects with a bivariate normal distribution and an unstructured (UN) covariance matrix while the treatment-by-time interaction is assumed to be a fixed effect. If there is a convergence issue under the assumed covariance structure (UN) for the random effect, then a variance-components covariance structure will be used. The within-subject errors are assumed to be independent and identically distributed normal random variables and are assumed to be independent of the random intercept and random slope. Within the framework of this model, a point estimate of the treatment group difference in the regression slope between each NGM621 group and the pooled Sham group will be provided. The corresponding two-sided 95% confidence interval and p-value for the point estimate will also be presented.

A hierarchical testing procedure will be used to control the family-wise type-I error rate associated with the tests of the two NGM621 groups (NGM621 Q4W vs pooled Sham and NGM621 Q8W vs pooled Sham). Specifically, the comparison between NGM621 Q4W and pooled Sham will be performed first. If this test is statistically significant at the 5% level, then the comparison between NGM621 Q8W and pooled Sham will be performed. If the first test is not statistically significant at the 5% level, then the comparison between NGM621 Q8W and pooled Sham will be considered exploratory.

### ***Sensitivity Analyses***

Sensitivity analyses will be performed to assess the robustness of the main estimator of the primary estimand. These sensitivity analyses will be performed with missing data imputed by the multiple imputation approach using the Markov Chain Monte Carlo (MCMC) method, a placebo-based pattern mixture model, and a tipping point method, respectively. The details of these analyses will be provided in the statistical analysis plan (SAP).

In addition, a sensitivity analysis will be performed using a nonlinear mixed effects model. In this model, the intercept is assumed to be a normal random variable, and the mean GA lesion area is assumed to be an exponential function of time with a separate slope (of time) for each treatment group. The within-subject errors are assumed to be independent and identically distributed normal random

---

---

variables and are assumed to be independent of the random intercept. The details of this analysis will be provided in the SAP.

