## 8 Statistical Considerations

A detailed statistical analysis plan (SAP) will be provided and finalized prior to the study database lock or unmasking. No discrepancies are expected between the SAP and the protocol. However, if there are discrepancies between this section of the protocol and the final SAP, the SAP will override the protocol.

In general, descriptive statistics including the number of non-missing observations (n), arithmetic mean (mean), standard deviation (SD), median, minimum (min), and maximum (max) will be presented by treatment group for continuous endpoints. Frequency and percentage distribution will be presented by treatment group for categorical endpoints.

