### **8.3.1.3 Sensitivity Analyses**

Sensitivity analyses will be performed to assess the robustness of the main estimator of the primary estimand. These sensitivity analyses will be performed with missing data imputed by the multiple imputation approach using the Markov Chain Monte Carlo (MCMC) method, a placebo-based pattern mixture model, and a tipping point method, respectively. The details of these analyses will be provided in the SAP.

CCI

The within-subject errors are assumed to be independent and identically distributed normal random variables, and are assumed to be independent of the random intercept. The details of this analysis will be provided in the SAP.

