#### **8.6 Sample Size Determination**

Subjects will be randomized in a 2:1:2:1 ratio to receive treatment with NGM621 Q4W, Sham Q4W, NGM621 Q8W, or Sham Q8W. Subjects from the two Sham groups will be pooled in the data analysis.

A sample size of 106 subjects per treatment group (i.e., 318 subjects in total) is expected to provide approximately 90% (NGM621 Q4W vs pooled Sham) and 85% (NGM621 Q8W vs pooled Sham) power to detect a statistically significant treatment group difference in the rate of change in GA lesion area over the 52 weeks of treatment. The power is estimated based on simulations assuming a mean GA lesion area of 8 mm^2 at baseline for all subjects, a common standard deviation of 4 mm^2 for GA lesion area, a linear slope of 2 mm^2 per year for the

pooled Sham group, 1.4 mm^2 per year for NGM 621 Q4W and 1.45 mm^2 per year for NGM 621 Q8W, a within-subject correlation of 0.95, a statistical significance level of 5% (two-sided), and a 10% of subject dropout rate. These assumptions are based on published data

CCI

CCI

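### The exponential sensitivity model has no patient-level random slope, so its model-based standard errors may be too small if growth rates vary substantially between patients

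*Combined protocol and SAP*

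**What the plan says.** The primary analysis (Synopsis, Main Estimation; Section 8.3.1.2) fits lesion area at baseline, Week 24 and Week 52 with patient-level variation in both level and growth: "The intercept and slope of time are assumed to be random effects with a bivariate normal distribution and an unstructured (UN) covariance matrix". The Synopsis fallback for non-convergence simplifies the covariance matrix but keeps the random slope.

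The exponential sensitivity model (Synopsis, Sensitivity Analyses) is different. There, "the intercept is assumed to be a normal random variable, and the mean GA lesion area is assumed to be an exponential function of time". Growth differs by arm only, "with a separate slope (of time) for each treatment group". Within-subject errors are independent and identically distributed. Section 8.3.1.3 is partly redacted, but its visible text also names only one random effect: the errors "are assumed to be independent of the random intercept".

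Section 8.6 bases power on "a common standard deviation of 4" mm², "a within-subject correlation of 0.95" and "a 10% of subject dropout rate". It gives no SD for growth rate. Details of the sensitivity analyses are left to the SAP, and under Section 8, if the two differ, "the SAP will override the protocol".

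**The concern.** A random-intercept model treats the visits of one patient, after removing the intercept, as carrying independent errors. If some patients grow faster than others in a way the intercept does not capture, their deviations at Weeks 24 and 52 run in the same direction. The model puts that variation into the independent error, counts it as more information about the growth rate than it is, and reports too small a standard error for the difference between arms.

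At stake is the value of this one model as evidence that the primary result does not depend on a straight-line mean. Its interval may be too narrow. Also, a result that differs from the primary cannot be put down to mean shape alone, because the random-effects structure changes at the same time.

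**Working it through.** **1. Inputs.** From Section 8.6: baseline mean 8 mm²; SD 4; correlation 0.95; slopes 2, 1.4 and 1.45 mm²/yr; 106 per group; 10% dropout; two-sided 5%. From Main Estimation: visits at t = 0, 24/52 and 1 year. The slope SD (τ) is an assumption, varied from 0 to 1.2 mm²/yr.

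**2. The plan's own power.** SD of one-year change = 4 × √(2 × (1 − 0.95)) = 1.265, so the variance is 1.6. With 106 × 0.9 = 95.4 per group, the standard error of a difference is 1.265 × √(2/95.4) = 0.183. Power is Φ(0.60/0.183 − 1.96) = 90.6% for Q4W and Φ(0.55/0.183 − 1.96) = 85.2% for Q8W, which match the stated 90% and 85%. Every case below therefore keeps the change variance at 1.6: τ² + 2σ² = 1.6, with σ² the residual variance. The SD stays at 4 at baseline and Week 52.

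**3. Closed form (linear analogue, complete data).** The sum of squares of time is Sxx = 0.501. The true slope variance per patient is σ²/Sxx + τ². An intercept-only model spreads τ²Sxx over two within-patient degrees of freedom, so it reports σ²/Sxx + τ²/2. With σ² = (1.6 − τ²)/2:

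| τ | σ² | true | reported | SE ratio | type I error |
|---|---|---|---|---|---|
| 0 | 0.800 | 1.597 | 1.597 | 1.00 | 5.0% |
| 0.6 | 0.620 | 1.598 | 1.418 | 0.94 | 6.5% |
| 0.9 | 0.395 | 1.598 | 1.193 | 0.86 | 9.0% |
| 1.1 | 0.195 | 1.599 | 0.994 | 0.79 | 12.2% |
| 1.2 | 0.080 | 1.600 | 0.880 | 0.74 | 14.6% |

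Type I error is 2 × (1 − Φ(1.96 × SE ratio)).

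**4. The exponential model itself.** Data were simulated with linear growth of 2 mm²/yr in all arms (no treatment effect), three arms of 106 and 10% dropout, half missing Week 52 and half missing Weeks 24 and 52. There were 2,000 data sets per case (Monte Carlo SE 0.5–0.8 points). Because the protocol text does not say how the intercept enters, two forms were fitted: a_i·exp(b_g·t) (multiplicative) and u_i + μ·exp(b_g·t) (additive). Entries are multiplicative / additive; the large-sample column has the same 10% dropout.

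| τ | share of change variance | implied baseline–Week 24 correlation | type I, model-based | type I, large sample | sandwich interval vs model-based |
|---|---|---|---|---|---|
| 0 | 0% | 0.950 | 4.3% / 5.8% | 3.7% / 5.0% | 7% narrower / same |
| 0.6 | 22% | 0.959 | 4.7% / 6.4% | 4.9% / 6.4% | 1% narrower / 6% wider |
| 0.9 | 51% | 0.970 | 7.1% / 8.5% | 6.9% / 8.9% | 7% / 15% wider |
| 1.1 | 76% | 0.980 | 9.6% / 11.8% | 9.4% / 12.1% | 16% / 26% wider |
| 1.2 | 90% | 0.985 | 11.3% / 14.3% | 11.2% / 14.5% | 22% / 34% wider |

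The additive large-sample column agrees with the closed form. Sandwich-based rejection lay between 4.5% and 6.0% over all ten cases.

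**5. A third reading.** If the intercept sits inside the exponent, exp(a_i + b_g·t), the ratio of model SE to empirical SD was 1.03, 0.97, 0.92 and 0.76 at τ = 0, 0.6, 0.9 and 1.1 (350 data sets per case, baseline limited to 2.5–17.5 mm²). The pattern is the same: material shortfall only when τ is large.

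**The case against.** The case against is substantial.

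- **A multiplicative intercept already carries growth variation.** Going from 8 to 10 mm², each patient grows by 25% of the intercept, so the implied between-patient growth SD is 0.25 × 4 = 1.0 mm²/yr, tied to lesion size. Only growth variation not explained by size is missing. This stands, and it is why that form shows no inflation at τ = 0.6.
- **The plan's figures imply no slope variation.** One SD and one correlation, read literally, give τ = 0. The larger cases move further from a single 0.95. This stands too; the sizes above are assumptions. The random slope in the primary model shows only that the plan allows for such variation.
- **The SAP may deal with it.** Details are left to the SAP, which takes precedence, and part of Section 8.3.1.3 is redacted. A missing variance estimator, or silence on how the intercept enters, is therefore no omission. The point rests on the random-effects structure that the protocol does state.
- **Dependence on linearity is checked elsewhere.** The Week 52 lesion-area analysis (Section 8.3.2) uses categorical visits and an unstructured covariance. With only three imaging visits, an intercept-only nonlinear model is a defensible economy. This limits the importance of the point but does not correct the interval.
- **The sandwich has a price and a limit.** With a multiplicative intercept and τ = 0 it moved rejection from 4.3% to 6.0%, and it does not separate mean shape from random effects. Both are true.

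**Conclusion.** The point holds in a conditional form, as something to consider. The stated structure may give intervals that are too narrow if growth rates vary substantially beyond what the intercept captures. With τ assumed at 0.9–1.2 mm²/yr (51–90% of the change variance), type I error is about 7–11% with a multiplicative intercept and 9–14% with an additive one. At τ = 0 there is essentially none.

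Three stronger readings are tempting, and the documents support none of them.

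- A reader might infer that any variation in growth makes the standard errors too small. The multiplicative case at τ = 0.6 shows otherwise.
- A reader who lets the log growth rate vary between patients on top of size-proportional growth can obtain 18–24% at τ = 0.8–1.0. That scenario does not respect the plan's variance: size-proportional growth alone adds (0.25 × 4)² = 1.0, so the change variance is already 1.6 + 1.0 = 2.6 at τ = 0, against the 1.6 that reproduces the stated power.
- A reader might infer that the trial's conclusion is at risk. The primary test, the hierarchical sequence and the Week 52 categorical-visit analysis do not use this model, and no decision rule depends on it.

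**What to change.** Report subject-level sandwich (robust) standard errors, with the matching interval and p-value, for the exponential model. This is one variance option and one sentence in the SAP. The cost is intervals up to about a third wider if growth rates vary greatly (34% in the additive case at τ = 1.2), and slightly liberal rejection, up to about 6%, if they do not.

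The sandwich corrects the interval only. To separate mean shape from random-effects structure, a supplementary fit with a subject-level random growth rate could be added. It is optional. In trial-sized data a multiplicative version gave usable fits in all 186 data sets tried (52, 56 and 78 at τ = 0.6, 0.9 and 1.2), with rejection of 7.7%, 3.6% and 3.8%. With a Monte Carlo SE of 2–4 points, that does not establish its error control.

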### **Secondary Efficacy Analyses**

Secondary efficacy endpoints include change from baseline at Week 52 in GA lesion area, the square root of GA lesion area, BCVA score, LLVA letter score, LLD in EDTRS letters at a starting distance of 4 meters, binocular reading speed (by MNRead or Radner reading charts), binocular critical print size (by MNRead or Radner reading charts), FRI composite score, and NEI VFQ-25, as well as change and percent change of CH50 from baseline. The change from baseline will be analyzed using a linear mixed-effects model. The model includes fixed effects for treatment, visit, treatment-by-visit interaction, and the baseline outcome value as a covariate. The covariance structure for this model will be assumed to be unstructured. If the model does not converge under this assumption, then a compound symmetry covariance structure will be used. Within the framework of this model, a point estimate of the treatment group difference at Week 52 between each NGM621 group and the pooled Sham group will be provided. The corresponding two-sided 95% confidence interval and p-value for the point estimate will also be presented.

### **Safety Analyses**

Adverse events will be coded using the Medical Dictionary for Drug Regulatory Activities (MedDRA). Ocular and systemic treatment-emergent adverse events (TEAEs) will be summarized by primary system organ class and preferred term. Actual values and change from baseline values for vital signs, clinical laboratory (hematology and chemistry) tests and other continuous variables (both ocular and non-ocular) will be summarized with descriptive statistics. Concomitant medications, physical examinations, and other categorical (safety) variables (both ocular and non-ocular) will be summarized with frequency and percentage distribution. All safety analyses will be performed using the Safety Analysis Set.

### **Pharmacokinetics Analyses**

Individual and mean serum NGM621 concentration–time data will be tabulated and plotted by cohort/dose level.

CCI

Additional PK analyses and/or summary statistics will be conducted as appropriate.

---

## 2 Introduction

### 2.1 Background

#### 2.1.1 Geographic Atrophy (GA)

Age-related macular degeneration (AMD) is a leading cause of blindness in the United States and the developed world. It is estimated that ~196 million (M) people have AMD globally and expected to increase to 288M by 2040 ([Wong 2014](#)). Approximately 15.7M have late stage disease, and this number is expected to increase to 26M by 2040 ([Wong 2014](#)).

There are two advanced forms of AMD: the neovascular/exudative form, also referred to as wet AMD, and the atrophic form, called geographic atrophy (GA). While neovascular AMD tends to cause more rapid and severe vision loss, it can be managed with one of several approved intravitreal (IVT) anti-VEGF therapies. GA causes more gradual, but relentlessly progressive and irreversible vision loss. It was previously estimated that GA accounted for one-tenth of the blindness due to AMD, while neovascular AMD accounted for the remainder ([Ferris 1984](#)). Due to the advent of anti-VEGF therapy, recent studies have reported that GA accounts for approximately one-quarter of legal blindness in the United Kingdom and the United States ([Holz 2014](#), [Boyer 2017](#)). An effective therapy for GA is one of the most important unmet needs in all of ophthalmology.

